To detect a change in median PFS from 5 months (for AI arm) to 9 months (with fulvestrant arm) would require about 124 patients (assuming 4-5 patients per month accrual, 5 months post-accrual follow-up, 5% two-sided alpha, 80% power, log rank testing). 84 PFS events are expected under the alternative hypothesis. Interim analysis will be performed when 42 PFS events are observed. Using O'Brien-Fleming stopping boundaries, we will stop for futility if the log rank test p-value $>$ 0.72 and stop for success if it is $<$ 0.004. Descriptive statistics and graphical analysis will be used to summarize patients' demographic and clinico-pathological characteristics, and efficacy outcomes. We will use mean (standard deviation) or median (range) to summarize continuous variables and frequency (percentages) for categorical variables. Graphical analysis, such as scatter plots with Lowess smoothers, will be used to assess the correlative structure of outcomes and compare MAF between fulvestrant and AI treated groups. The Pearson correlation, or its non-parametric analogue, the Spearman correlation, will be used to estimate the linear correlation among variables. Radiographic response rate (partial response + complete clinical response) will be estimated and reported with a 95% CI.

Control	Experimental	
Median	Median	Power
5	6	15%
5	7	38%
5	8	63%
5	9	81%
5	10	91%
5	11	96%
5	12	98%

REFERENCES:

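### Section 9's interim figures (look at 42 events, 84 expected events, O'Brien-Fleming, success at p < 0.004, futility at p > 0.72) do not belong to one design, and no final event count or final significance level is stated

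*Combined protocol and SAP*

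**What the plan says.** All of this is in Section 9, Statistical Considerations, of the combined protocol and SAP.

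- Design inputs: median PFS of 5 months on AI against 9 months on fulvestrant, "5% two-sided alpha, 80% power, log rank testing", and about 124 patients, "assuming 4-5 patients per month accrual, 5 months post-accrual follow-up".
- Events: "84 PFS events are expected under the alternative hypothesis".
- Interim look: "Interim analysis will be performed when 42 PFS events are observed".
- Boundary: "Using O'Brien-Fleming stopping boundaries", the trial stops for futility if the log-rank p-value exceeds 0.72, "and stop for success if it is $<$ 0.004".
- The power table gives 81% for medians of 5 and 9 months.

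The section does not state the event count that triggers the final analysis, the information fraction at the interim, which version of O'Brien-Fleming is meant, or the nominal level of the final test.

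**The concern.** The only event total printed is 84, and 42 is exactly half of it, so a reader takes the look to be at half the information. For a given version, alpha and information fraction, an O'Brien-Fleming cut-off is a determined number. At one half, none of the usual versions gives 0.004.

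This threshold can end the trial early with a claim of success, and the level left for the final test depends on it. If 42, 84 and 0.004 come from different designs, nobody can work out from the plan which final level keeps the overall error at 5%. The monitoring board would also be applying a cut-off that it cannot trace to the boundary named.

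**Working it through.** **Inputs from Section 9.** Two-sided alpha 0.05, power 80%, medians 5 and 9 months, interim at 42 events, 84 expected events, cut-offs 0.004 and 0.72, 124 patients, 4 to 5 per month, 5 months of follow-up after accrual.

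**Assumptions not in the plan.** 1:1 allocation, the usual normal approximation (log-rank Z with drift ln(9/5)·√d/2 at d events), and two-sided p-values. The event projection in step 5 also assumes exponential PFS and no dropout. Alpha is computed without credit for futility stopping.

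**1. Events and power.** The planned hazard ratio is 5/9 = 0.556, and ln(9/5) = 0.5878. Events for 80% power: 4 × (1.960 + 0.842)² / 0.5878² = 90.9, so 91. Power at 84 events: Φ(0.5878 × √84 / 2 − 1.960) = 76.8%. So 84 is not the number needed for the stated 80%, nor for the table's 81%.

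**2. Success cut-off at 42/84, t = 0.50.** The two statistics have correlation √t.

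- Classic: find c so that crossing c/√t at the interim or c at the end has total probability 0.05. Result: c = 1.977, interim z = 2.797, p = 0.0052, final p = 0.0480.
- Lan-DeMets, 0.025 per side: 4(1 − Φ(2.2414/√t)) = 0.0031 (unrounded 0.00305, z = 2.963).
- Spending function applied to the two-sided 0.05: 2(1 − Φ(1.960/√t)) = 0.0056.
- Pampallona-Tsiatis form with binding futility: 0.0062.

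None rounds to 0.004.

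**3. Futility cut-off at 42/84.** O'Brien-Fleming-type beta spending with beta = 0.20 gives 2(1 − Φ(1.2816/√t)) = 0.0699 at t = 0.50. The drift at 42 events is 0.5878 × √42 / 2 = 1.905. The futility z is 1.905 + Φ⁻¹(0.0699) = 0.428, a two-sided p of 0.67. If the drift is set to give 80% power at 84 events, z = 0.505 and p = 0.61. Neither is 0.72.

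**4. Which final total fits the printed cut-offs?** The interim is held at 42 events and futility uses the planned hazard ratio.

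| Final events | t | Classic | Lan-DeMets, 0.025 per side | Spending on two-sided 0.05 | Futility p |
|---|---|---|---|---|---|
| 84 | 0.500 | 0.0052 | 0.0031 | 0.0056 | 0.67 |
| 88 | 0.477 | 0.0043 | 0.0024 | 0.0046 | 0.70 |
| 90 | 0.467 | 0.0039 | 0.0021 | 0.0041 | 0.72 |
| 91 | 0.462 | 0.0037 | 0.0019 | 0.0039 | 0.73 |
| 98 | 0.429 | 0.0026 | 0.0012 | 0.0028 | 0.79 |

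At about 90 events both printed figures come out together, and 90 is next to the 91 of step 1.

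**5. Events the stated timeline would yield.** Accrual lasts 124/4 = 31 or 124/5 = 24.8 months. With uniform accrual over A months, 5 months of follow-up and hazard λ = ln 2 / median, the event probability in an arm is 1 − (e^(−5λ) − e^(−(A+5)λ))/(λA). With 62 patients per arm this gives 96 to 101 events.

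**6. Effect on error and on early stopping.**

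| Final events | Overall alpha, 0.004 then 0.05 | Final level that keeps 5% with 0.004 |
|---|---|---|
| 84 | 0.0514 | 0.0486 |
| 91 | 0.0516 | 0.0484 |
| 98 | 0.0518 | 0.0482 |

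The observed hazard ratio needed at 42 events is exp(−2z/√42). It is 0.411 for p = 0.004 (z = 2.878) and 0.401 for the per-side Lan-DeMets value at 42/84. The chance of an early success stop at the planned hazard ratio is P(N(1.905, 1) > z): 16.5% with 0.004, 18.6% with the classic value at 42/84, and 14.5% with the Lan-DeMets value at 42/84.

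**The case against.** The best defence is that the plan calls 84 an expected number and never says the final analysis takes place at 84. With a maximum of 88 to 91 events, 0.004 is a genuine O'Brien-Fleming value: the classic form gives 0.0043 to 0.0037, and spending on the two-sided 0.05 gives 0.0041 at 90. The futility figure fits there as well. This stands, and it limits the point. A reader might infer that the success rule is not an O'Brien-Fleming rule at all; the documents do not support that. But the defence needs a total of about 90 that the plan nowhere prints, and it leaves 84 unexplained.

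One could explain 84 as an average that allows for early stopping. Under the planned effect the trial stops at the interim with probability 0.165 + 0.049 = 0.214, so an average of 84 needs a maximum of about (84 − 0.214 × 42)/0.786 = 95 to 96 events. At those totals the classic cut-off is 0.0030 to 0.0029, so this reading does not recover 0.004 either.

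A second tempting reading is that 0.004 is looser than the named boundary and spends too much alpha early. Against every version in the table, that holds only if the final total is about 98, a projection that assumes exponential PFS and no dropout. Against the printed 84, 0.004 lies between the two standard values and is stricter than the classic one. It causes no inflation if the final level is matched to it.

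It is also fair to say that a fixed interim cut-off at a fixed event count is legitimate, that this is a randomized Phase II trial, and that the numerical effect is small. All of that stands. It bears on how much the point matters, not on whether the printed figures agree.

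**Conclusion.** The point holds as an inconsistency with missing information. The 42-event look, the 84 events, the named boundary and the two cut-offs cannot all come from one design. Either 84 is the final count and neither 0.004 nor 0.72 matches it, or the cut-offs were computed for about 90 events and the plan does not say so. The second explanation is an inference from the figures.

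The consequence is modest. Overall alpha is 0.0514 to 0.0518 if the final test is run at 0.05, and exactly 5% if the final level is set at 0.0486 to 0.0482. The chance of an early success stop differs by about two percentage points either way between 0.004 and the standard values at 42/84. The correction is still worth making before interim data are seen, because the threshold can end the trial. The conclusion rests on 1:1 allocation, the normal approximation and two-sided p-values.

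**What to change.** In Section 9, state one event count for the final analysis, the information fraction at the interim and the version of O'Brien-Fleming. Take the interim success cut-off, the futility cut-off and the final nominal level from that one run. Any of these would be coherent:

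- Classic at 42/84: success at p < 0.0052, final level 0.0480, and the power statement changed to the 76.8% that 84 events give.
- Lan-DeMets with 0.025 per side at 42/84: success at p < 0.0031, with the final level from the same run and the same change to the power statement.
- Classic at 42/90 or 42/91: 0.004 stays, the final level is about 0.0485, and the 84 is corrected.
- 0.004 kept as a fixed interim cut-off: print the matched final level in place of 0.05 (0.0486 at 84 events, 0.0484 at 91, 0.0482 at 98).

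The choice of version belongs to the sponsor, since the plan names none. The futility value should be re-derived for whichever total is chosen; with beta spending at the planned hazard ratio it is about 0.67 at 84 and 0.72 at 90.

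The cost is one boundary run and a few lines of protocol and SAP text. The downside is a final cut-off slightly below 0.05 and, depending on the version, a slightly different chance of stopping early.

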2.3. Secondary Objectives

- To assess ctDNA *ESR1* mutant allele fraction (MAF) and kinetics with fulvestrant compared with AI
- To assess the prevalence of *ESR1* mutations in patients with secondary resistance to endocrine therapy
- To correlate ctDNA with CA 15-3 tumor marker changes
- To assess overall survival (OS) with transition to fulvestrant compared with continuing AI therapy in patients with emergence of *ESR1* mutations
- To assess PFS and time to next treatment (TTNT) on next line of therapy after progression on fulvestrant vs. AI in combination with CDKI

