6.2. Evaluation during study

Follow up laboratory assessments should be performed as per standard of care for palbociclib, ribociclib, abemaciclib, and fulvestrant

- Physical examination (including vital signs, weight, performance status)
- Patients will undergo restaging with complete imaging (CT CAP and bone scan) approximately every 3-4 cycles of therapy for the first 12 months and every 3-6 months thereafter until progression.
- Exploratory ctDNA blood draws (Guardant360 StreckTM cell preservation tubes (8-10 mL x 2 per blood draw) will be performed at Cycle 2, Cycle 4 and Cycle 12. These will be banked at MDACC. ctDNA will be drawn on the same date as standard of care labs assessments.
- End of Treatment/Progression ctDNA Blood draw (Guardant360 StreckTM cell preservation tubes (8-10 mL x 2 per blood draw).

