8. BIOMARKER AND CORRELATIVE STUDIES

ctDNA analysis

To identify *ESR1* alterations, patients will have mandatory ctDNA assessment prior to randomization. In addition, to assess mutant allele fraction/ somatic allele burden (SAB) plasma for ctDNA would be obtained at 4, 12 weeks, and at progression. Blood draw for ctDNA would be stored in Guardant360 StreckTM cell preservation tubes (8-10 mL x 2 per blood draw). Where possible, blood samples for ctDNA will be drawn from patients scheduled to have venipuncture for standard of care labs assessments for clinical care. Patients with activating *ESR1* mutations will be treated until radiological disease progression. To characterize candidate mechanisms of resistance, Guardant 360 ctDNA analyses will be performed at disease progression and compared with pre-treatment ctDNA analyses. Specifically, we will evaluate alterations in *TP53* and *PIK3CA* and correlate with PFS. We will also evaluate for acquired *RB* mutations as well as other emergent genomic alterations with exposure to CDK inhibitors. We will correlate ctDNA dynamics with changes in CA 15-3 tumor marker. We will also correlate ctDNA dynamics and velocity with responses seen on imaging.

Solid Tumor Genomic Assay 2018									
Hotspot Genes				Full-Length		Copy Number		Gene Fusions	
n = 87				n = 48		n = 47		n = 51	
AKT1	FGFR1	MAP2K1	RAF1	ARID1A	NOTCH3	AKT1	IGF1R	AKT2	MYBL1
AKT2	FGFR2	MAP2K2	RET	ATM	PALB2	AKT2	KIT	ALK	NF1
AKT3	FGFR3	MAP2K4	RHEB	ATR	PIK3R1	AKT3	KRAS	AR	NOTCH1
ALK	FGFR4	MAPK1	RHOA	ATRX	PMS2	ALK	MDM2	AXL	NOTCH4
AR	FLT3	MAX	ROS1	BAP1	POLE	AR	MDM4	BRAF	NRG1
ARAF	FOXL2	MDM4	SF3B1	BRCA1	PTCH1	AXL	MET	BRCA1	NTRK1
AXL	GATA2	MED12	SMAD4	BRCA2	PTEN	BRAF	MYC	BRCA2	NTRK2
BRAF	GNA11	MET	SMO	CDK12	RAD50	CCND1	MYCL	CDKN2A	NTRK3
BTK	GNAQ	MTOR	SPOP	CDKN1B	RAD51	CCND2	MYCN	EGFR	NUTM1
CBL	GNAS	MYC	SRC	CDKN2A	RAD51B	CCND3	NTRK1	ERBB2	PDGFRA
CCND1	H3F3A	MYCN	STAT3	CDKN2B	RAD51C	CCNE1	NTRK2	ERBB4	PDGFRB
CDK4	HIST1H3B	MYD88	TERT	CHEK1	RAD51D	CDK2	NTRK3	ERG	PIK3CA
CDK6	HNF1A	NFE2L2	TOP1	CREBBP	RB1	CDK4	PDGFRA	ESR1	PPARG
CHEK2	HRAS	NRAS	U2AF1	FANCA	RNF43	CDK6	PDGFRB	ETV1	PRKACA
CSF1R	IDH1	NTRK1	XPO1	FANCD2	SETD2	CDKN2A	PIK3CA	ETV4	PRKACB
CTNNB1	IDH2	NTRK2		FANCI	SLX4	CDKN2B	PIK3CB	ETV5	PTEN
DDR2	JAK1	NTRK3		FBXW7	SMARCA4	EGFR	PPARG	FGFR1	RAD51B
EGFR	JAK2	PDGFR		MLH1	SMARCB1	ERBB2	RICTOR	FGFR2	RAF1
ERBB2	JAK3	PDGFRB		MRE11A	STK11	ESR1	TERT	FGFR3	RB1
ERBB3	KDR	PIK3CA		MSH2	TP53	FGF19	TSC1	FGR	RELA
ERBB4	KIT	PIK3CB		MSH6	TSC1	FGF3	TSC2	FLT3	RET

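### The between-arm comparison of ESR1 mutant allele fraction, a secondary objective, is planned as graphics only, with no effect measure, time point, interval or stated use of baseline

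*Combined protocol and SAP*

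**What the plan says.** Section 2.3 lists as its first secondary objective "To assess ctDNA *ESR1* mutant allele fraction (MAF) and kinetics with fulvestrant compared with AI", and Section 2.4 lists MAF first among the secondary endpoints. This is a declared comparison between randomised arms.

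The only analysis in Section 9 that names MAF by arm is the sentence that sets out to "compare MAF between fulvestrant and AI treated groups", and its method is graphical: "Graphical analysis, such as scatter plots with Lowess smoothers, will be used to assess the correlative structure of outcomes and compare MAF" between the two groups. The neighbouring sentences are generic. One reads "We will use mean (standard deviation) or median (range) to summarize continuous variables"; another offers a Pearson or Spearman coefficient that "will be used to estimate the linear correlation among variables". By contrast, the PFS treatment comparison gets a Cox estimate with a 95% CI, OS is to be analysed in the same way, and the radiographic response rate gets a 95% CI.

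On sampling, Section 8 says that "patients will have mandatory ctDNA assessment prior to randomization", and Section 3.1 makes an ESR1 mutation on ctDNA an entry condition. Section 6.2 says that on-treatment draws "will be performed at Cycle 2, Cycle 4 and Cycle 12". Appendix 1 agrees and has these samples banked and assayed when the study concludes. Section 8 instead lists draws at 4 weeks, 12 weeks and progression. Section 6.2, Section 8 and Appendix 1 all include a sample at progression.

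**The concern.** A plot with a smoother, arm-wise means or medians, and correlation coefficients do not together yield a between-arm difference or ratio with an interval. The objective could be reported without any statement of how large the MAF effect is or how precisely it is known. Time point and metric would also remain open until the banked samples are assayed.

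Two features of the design make this worth settling now. First, every randomised patient should have a positive baseline result, which is usually the strongest available covariate for a later MAF, yet Section 9 does not say how it enters. Second, protocol therapy ends at progression (Section 5.5), so a sample tied to a late cycle is available mainly from patients who have not progressed. If the arms differ in PFS, as the design assumes, those patients are a different selection in each arm. Section 1.2 itself reports that rising circulating ESR1 at 3 months was followed by progression, so a link between MAF and PFS is plausible here.

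**Working it through.** **Plan's own figures.** The documents give no figure for the MAF comparison, so the inputs come from the PFS design in Section 9: medians of 5 and 9 months and 124 patients. Allocation is not stated; 1:1 (62 per arm) is assumed, with exponential PFS. These assumptions fit the design:

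- With 5 patients per month, accrual takes A = 124/5 = 24.8 months, with F = 5 months of follow-up.
- The event probability is p(m) = 1 − [exp(−λF) − exp(−λ(A+F))]/(λA), with λ = ln 2/m. This gives p(5) = 0.859 and p(9) = 0.697, so 62 × 1.556 = 96.5 events.
- Fixed-design power is Φ(|ln(5/9)| × √96.5/2 − 1.96) = Φ(0.93) = 82.3%, against 81% in the plan's table.
- Simulating the stated interim rule at 42 events gives 80.3% to 80.7% power and an average of 84.8 events, close to the plan's 84.

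**Who is left at each draw.** The cycle length is 28 days (Section 7.1). Taking Day 1 of each cycle, the times are 4, 12 and 44 weeks, or 0.92, 2.76 and 10.12 months. The progression-free share is 0.5^(t/median).

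| Draw | AI | Fulvestrant |
|---|---|---|
| Cycle 2 | 0.5^(0.92/5) = 88% (55 of 62) | 0.5^(0.92/9) = 93% (58 of 62) |
| Cycle 4 | 0.5^(2.76/5) = 68% (42) | 0.5^(2.76/9) = 81% (50) |
| Cycle 12 | 0.5^(10.12/5) = 25% (15) | 0.5^(10.12/9) = 46% (28) |

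A Cycle 12 comparison therefore rests on about 15 + 28 = 43 of 124 patients. These shares assume no dropout and progression recognised when it occurs.

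**What selection alone could do at Cycle 12.** In a simulation with no drug effect on MAF and an assumed PFS log hazard ratio of 0.3 to 0.8 per SD of log(MAF), mean log(MAF) among those remaining was 0.16 to 0.23 SD higher on fulvestrant, which counts against fulvestrant. With a log hazard ratio of 0 the difference was nil.

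**What baseline adjustment gains.** If baseline and follow-up log(MAF) correlate at r, the variance of the adjusted arm contrast is multiplied by 1 − r², and the interval width by √(1 − r²). The documents give no r, so 0.5 to 0.7 is assumed.

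- r = 0.5: variance falls by 0.25 (25%); the interval narrows by 1 − √0.75 = 13%.
- r = 0.7: variance falls by 0.49 (49%); the interval narrows by 1 − √0.51 = 29%.

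The documents give no SD for MAF, so the 95% CI half-width is in SD units: 1.96 × √[(1/n1 + 1/n2)(1 − r²)].

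- Cycle 2 (54.6 and 57.8 patients before rounding): 0.37 at r = 0, 0.32 at r = 0.5, 0.26 at r = 0.7.
- Cycle 12 (15.2 and 28.4): 0.62, 0.54 and 0.44.

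**The case against.** The best defence is that this is a biomarker objective in a phase II trial, that the on-treatment draws are themselves described as exploratory in Section 6.2 and Appendix 1, and that descriptive analysis is acceptable at that level. This limits the severity. It does not answer the point that the comparison is a listed secondary objective, or that an estimate with an interval costs almost nothing.

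Three stronger readings are tempting, and the documents do not support them.

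- *That the plan ignores baseline MAF.* The objective speaks of kinetics, and Section 8 speaks of dynamics and velocity and compares progression samples with pre-treatment ones. Some use of baseline is implied. What is missing is how it enters the arm comparison.
- *That late samples exist only for non-progressors.* Patients who progress give a sample at progression. The selection concerns the scheduled Cycle 12 draw.
- *That the planned smoother is biased.* Section 9 names no axes and offers the smoother only as an example. Selection comes from the visit schedule, not from the graph, and produces bias only if MAF is related to PFS. Baseline adjustment alone would not remove it; choosing an early time point limits it.

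It is also fair that the Cycle 2 and Cycle 4 shares treat progression as detected continuously. Restaging is about every 3 to 4 cycles, and on-treatment imaging first appears under Cycle 4 in Appendix 1, so fewer samples would probably be lost by then than the table shows. That strengthens the case for Cycle 2.

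**Conclusion.** The point holds as a gap in the analysis of one secondary objective: Section 9 gives graphics where an estimate is needed, and leaves effect measure, time point, interval and baseline handling unstated. At Cycle 12 the arms would be compared on differently selected subsets. That is a bias if MAF relates to PFS, and otherwise only a loss of precision. The size of the selection rests on the design medians, exponential PFS, 1:1 allocation and no dropout; the gain from adjustment rests on the assumed correlation.

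Nothing here touches the primary PFS analysis, the sample size or the interim rule. Label: free improvement, minor severity.

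**What to change.** In Section 9, make the main MAF analysis a linear model of log(MAF) at Cycle 2 (week 4) on arm and baseline log(MAF), with the stratification factors where usable. The prior adjuvant endocrine therapy factor has levels only for tamoxifen and AI, so say how patients without such therapy are coded. Report the ratio of geometric means with a 95% CI. Week 4 appears in both sampling schedules, so this choice does not depend on how they are reconciled.

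State in advance:

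- how several ESR1 variants in one patient are combined, for example sum or maximum, since Section 1.2 notes that polyclonal mutations are common;
- how undetected values are handled. The documents give no detection limit, and any substitution rule is one choice among several, so add a sensitivity analysis such as a rank-based or censored-value model.

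Keep the Cycle 4, Cycle 12 and progression samples, and the plots, as descriptive support. Reconcile Section 6.2 and Appendix 1 (Cycles 2, 4 and 12, and progression) with Section 8 (4 weeks, 12 weeks and progression).

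The cost is SAP wording and one model with its sensitivity analysis. The baseline and Cycle 2 samples are already in the plan, and the Cycle 2 sample is already due for assay at study conclusion. The text should be fixed before those results are read.

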Appendix 1 Schedule of clinical assessments

Evaluation	Screening	Cycle 1	Cycle 2	Cycle 4	Cycle 12	End of treatment/ Progression
Physical exam, Vital Signs	X ^a					
ECOG PS	X ^a					
Hematology and Chemistry	Z					
Coagulation (PT/PTT/INR)	Z					
Pregnancy Test (urine)*	X					
Liquid Biopsy **	X**		X***	X***	X***	X**
Concomitant medications	X ^a					
Fulvestrant^d administration		X	X	X	X	
Imaging	X ^b			X	X	X
Tumor marker	X		X	X ^c	X	

* For women of child bearing age. Repeated at the discretion of treating physician

^zLabs and clinical monitoring should be performed as per standard of care for CDK4/6 with AI/fulvestrant use

^{**} Guardant ctDNA assessments are collected at screening (for baseline *ESR1* assessment), at progression.

^{***}Exploratory samples for ctDNA assessment will be collected at Cycle 2, Cycle 4 and Cycle 12 and will be banked at MDACC and processed at Guardant Health at the time of study conclusion.

^a All medications (other than study drug) taken within 28 days of starting study treatment through the 30-day safety follow up visit should be reported on the CRF.

^b Tumor imaging (CT/Bone scan) will be performed approximately every 3-4 cycles of therapy for the first 12 months and every 3-6 months thereafter until progression. Tumor imaging should be performed at MD Anderson.

^c Tumor markers (CA 15-3) performed approximately every 3 cycles (12 weeks) until disease progression in coordination with routine labs and imaging

^d Fulvestrant administration for patients randomized to the fulvestrant arm only (+/- 7 days). Second dose of fulvestrant to be administered at C1D15. Control patients would continue the treatment they were already on (CDK inhibitor in combination with aromatase inhibitors). Fulvestrant can be administered under the supervision of treating physician locally.

Proprietary of MD Anderson Cancer Center

Protocol 2018-0287

January 8, 2020
